#### 8.4.3 Sample Labeling

Each tube must be labeled with the patient's study registration number, the study I.D (APEC1621A), and the date and time the sample was drawn. Data should be recorded on the appropriate transmittal form found in RAVE, which must accompany the sample(s).

#### 8.4.4 Sample Shipping Instructions

Specimen should be shipped at room temperature to the BPC (address below). Upon arrival separation, extraction, and storage of plasma and cellular DNA will be performed. Samples should be shipped from Monday through Friday for Tuesday through Saturday delivery. If blood is collected over the weekend or on the day before a holiday, the sample should be stored in a refrigerator until shipped on the next business day. Ship by FedEx Priority Overnight using the COG FedEx account. Blood samples should be shipped the same day as collection, ship blood for Saturday delivery if shipped on Friday.

Ship specimens to the following address:

Biopathology Center  
Nationwide Children's Hospital  
Protocol APEC1621A– Peds MATCH\*  
[name]  
[name]  
[contact]  
[contact]  
Email:[[contact]](mailto:[contact])

\*Labeling is extremely important for this project. Packages **must** be labeled "Peds MATCH" in order to expedite processing at the BPC. Be sure to include the room number. Packages received without the room number may be returned to the sender.

## 9.0 AGENT INFORMATION

### 9.1 **Larotrectinib** 09/28/22

(larotrectinib sulfate, Vitrakvi®, LOXO-101, BAY 2757556) NSC# 788607,  
IND# XXXXXXXXXX

#### 9.1.1 Structure and molecular weight

Larotrectinib sulfate is a small molecule with an empirical formula of  $C_{21}H_{24}F_2N_6O_6S$  and a molecular weight of 526.52 (hydrogen sulfate salt), 428.4 (free base). The chemical name is (S)-N-(5-((R)-2-(2,5-difluorophenyl)pyrrolidin-1-yl)pyrazolo[1,5-a]pyrimidin-3-yl)-3-hydroxypyrrrolidine-1-carboxamide hydrogen sulfate.

Larotrectinib is an ATP-competitive, selective inhibitor of the tropomyosin-related kinase (TRK) family of neurotrophin receptors, demonstrating inhibition of all three known TRK receptors (TRKA, TRKB and TRKC). In normal tissue, activated TRK receptor signaling may stimulate cellular growth, survival and differentiation. TRK receptors are encoded by NTRK genes; NTRK1, NTRK2, and NTRK3. NTRK gene fusions appear to be oncogenic and inhibition of TRK receptors may provide benefit to patients with malignancies due to oncogenic alterations in the NTRK genes.

#### 9.1.2 Supplied by:

Bayer AG and distributed by the Pharmaceutical Management Branch, CTEP, DCTD, NCI. **Do not use commercial supply**

#### 9.1.3 Formulation

- 25 mg capsules are opaque white, size 2, hard gelatin capsules containing 25 mg of Larotrectinib sulfate. The capsules contain no excipients. Capsules are supplied in 60-count, 72-count or 100-count HDPE bottles with induction seals and child-resistant plastic caps.
- 100 mg capsules are opaque white, size 0, hard gelatin capsules containing 100 mg of Larotrectinib sulfate. The capsules contain no excipients. Capsules are supplied in 60-count, 72-count or 100-count HDPE bottles with induction seals and child-resistant plastic caps.
- 50 mL or 100 mL liquid oral solution containing 20 mg/mL of larotrectinib sulfate filled into 60 mL (ORA-SWEET free) or 100 mL. Kylix, amber type III glass bottles, PP28 neck, with a 28 mm child resistant cap and tamper evident closure with Triseal liner.
  - The 50 mL bottle of oral solution is a colorless to yellow or orange or brownish liquid containing the following inactive ingredients: purified water, USP; Kleptose HPB Parenteral Grade, USP; Citric Acid, anhydrous, USP; Flavor strawberry, specification; Sodium benzoate, NF; Sodium citrate, USP; Sucralose, USP/NF
  - The 100 mL bottle of oral solution is a colorless to clear yellow to orange liquid containing the following inactive ingredients: purified water, USP; Kleptose HPB Parenteral Grade, USP; ORA-SWEET®; Sodium Citrate, Dihydrate, Granular, USP; 231a12 Natural Masking Type Flavor (Abelei); 231a39 Natural Bitterness Masking Type Flavor (Abelei); Bitterness Masking Flavor, Nat (FONA - Liquid); FONATECH® Taste Modifier Flavor, Nat

- A site-supplied 28 mm LDPE (e.g., Comar® product number 22-0198; B Braun Exadoral®) or polypropylene press-in bottle adapter is required for use with an oral syringe for dosing purposes.

#### 9.1.4 Storage

Store capsules at room temperature below 30° (86°F). Store liquid oral solution refrigerated at 2°C to 8°C (36°F to 46°F). Do not freeze

If a storage temperature excursion is identified, promptly return larotrectinib capsules to controlled room temperature and larotrectinib liquid oral solution to refrigerated temperature and quarantine the supplies. Provide a detailed report of the excursion (including documentation of temperature monitoring and duration of the excursion) to [[contact]](mailto:[contact]) for determination of suitability.

#### 9.1.5 Stability

Bottle labels contain an expiration date. Larotrectinib sulfate capsules for a cycle may be counted out and repackaged from the manufacturer-supplied HDPE bottle into a pharmacy-supplied HDPE bottle for dispensing purposes. Instruct patients to store the prescription container away from areas of high heat and humidity.

Larotrectinib sulfate liquid oral solution is to be dispensed in the manufacturer's container as a whole bottle. After opening, store capsules below 30°C (86°F) and oral solution refrigerated at 2°C to 8°C (36°F to 46°F) for up to 30 days.

#### 9.1.6 Administration

See [Section 6.0](#) for dose modifications and [Section 5.0](#) Treatment section of the protocol for dosing and administration details. Larotrectinib is administered orally or via NG- or G-tube and may be taken without regard to food. Larotrectinib sulfate may be taken without regard to food. Capsules are to be swallowed whole. Do not chew, crush or open capsules. **Please note the maximum dose of 100 mg per dose BID.**

#### 9.1.7 Potential Drug Interactions

Larotrectinib is a substrate of cytochrome P450 (CYP) 3A, P-glycoprotein (P-gp) and breast cancer resistance protein (BCRP). Co-administration of larotrectinib with strong CYP3A inhibitors, P-gp and BCRP inhibitors increases larotrectinib plasma concentrations. Co-administration of larotrectinib with strong CYP3A and P-gp inducers decreases larotrectinib plasma concentrations. Avoid concomitant use of strong CYP3A inhibitors or inducers for 14 days prior to enrollment through the end of protocol therapy ([Appendix II](#)). Avoid grapefruit or grapefruit juice as these may also increase plasma concentrations of larotrectinib.

If feasible, avoid concomitant administration with strong P-gp or BCRP inhibitors and strong P-gp inducers.

Larotrectinib inhibits CYP3A weakly both in vitro and in vivo. Exercise caution with concomitant use of CYP3A substrates with narrow therapeutic range (e.g. alfentanil, cyclosporine, dihydroergotamine, ergotamine, fentanyl, pimozide, quinidine, sirolimus, or tacrolimus; [Appendix II](#)) in patients taking larotrectinib. If concomitant use of these CYP3A substrates with narrow therapeutic range is

required in patients taking larotrectinib, additional toxicity monitoring and/or dose modification of the CYP3A substrates may be required due to adverse reactions.

Antacid use does not significantly alter the pharmacokinetics of larotrectinib.

#### 9.1.8 Patient Care Considerations

Based on the mechanism of action, fetal harm cannot be excluded when administering larotrectinib to a pregnant woman.

Advise female and male patients of reproductive potential to use highly effective contraception during treatment with larotrectinib and for at least one month after the final dose.

Because of the unknown risk of larotrectinib in nursing infants, advise a nursing woman to discontinue breastfeeding during treatment with larotrectinib and for 3 days (6 plasma half-lives of larotrectinib and its metabolites) following the final dose.

#### 9.1.9 Larotrectinib Toxicities

#### Comprehensive Adverse Events and Potential Risks list (CAEPR) for Larotrectinib sulfate (BAY 2757556, LOXO-101, NSC 788607)

The Comprehensive Adverse Events and Potential Risks list (CAEPR) provides a single list of reported and/or potential adverse events (AE) associated with an agent using a uniform presentation of events by body system. In addition to the comprehensive list, a subset, the Specific Protocol Exceptions to Expedited Reporting (SPEER), appears in a separate column and is identified with bold and italicized text. This subset of AEs (SPEER) is a list of events that are protocol specific exceptions to expedited reporting to NCI (except as noted below). Refer to the 'CTEP, NCI Guidelines: Adverse Event Reporting Requirements' [http://ctep.cancer.gov/protocolDevelopment/electronic\\_applications/docs/aeguidelines.pdf](http://ctep.cancer.gov/protocolDevelopment/electronic_applications/docs/aeguidelines.pdf) for further clarification. Frequency is provided based on 388 patients. Below is the CAEPR for Larotrectinib sulfate (BAY 2757556, LOXO-101).

**NOTE:** Report AEs on the SPEER **ONLY IF** they exceed the grade noted in parentheses next to the AE in the SPEER. If this CAEPR is part of a combination protocol using multiple investigational agents and has an AE listed on different SPEERs, use the lower of the grades to determine if expedited reporting is required.

Version 2.3, May 12, 2022

Adverse Events with Possible Relationship to Larotrectinib sulfate (BAY 2757556, LOXO-101) (CTCAE 5.0 Term) [n= 388]			Specific Protocol Exceptions to Expedited Reporting (SPEER)
Likely (>20%)	Less Likely (<=20%)	Rare but Serious (<3%)	
BLOOD AND LYMPHATIC SYSTEM DISORDERS			
	Anemia		Anemia (Gr 2)
GASTROINTESTINAL DISORDERS			
	Abdominal pain		Abdominal pain (Gr 2)
	Constipation		Constipation (Gr 2)
	Diarrhea		Diarrhea (Gr 2)
	Nausea		Nausea (Gr 2)
	Vomiting		Vomiting (Gr 2)

GENERAL DISORDERS AND ADMINISTRATION SITE CONDITIONS		
	Edema limbs	Edema limbs (Gr 2)
	Fatigue	Fatigue (Gr 2)
	Fever	Fever (Gr 2)
		Gait disturbance
INVESTIGATIONS		
	Alanine aminotransferase increased	Alanine aminotransferase increased (Gr 2)
	Aspartate aminotransferase increased	Aspartate aminotransferase increased (Gr 2)
	Neutrophil count decreased	Neutrophil count decreased (Gr 2)
	Weight gain	Weight gain (Gr 2)
MUSCULOSKELETAL AND CONNECTIVE TISSUE DISORDERS		
	Myalgia	Myalgia (Gr 2)
NERVOUS SYSTEM DISORDERS		
	Dizziness	Dizziness (Gr 2)
		Paresthesia
RESPIRATORY, THORACIC AND MEDIASTINAL DISORDERS		
	Cough	Cough (Gr 2)
	Dyspnea	Dyspnea (Gr 2)

This table will be updated as the toxicity profile of the agent is revised. Updates will be distributed to all Principal Investigators at the time of revision. The current version can be obtained by contacting [[contact]](mailto:[contact]). Your name, the name of the investigator, the protocol and the agent should be included in the e-mail.

**Adverse events reported on Larotrectinib sulfate (BAY 2757556, LOXO-101) trials, but for which there is insufficient evidence to suggest that there was a reasonable possibility that Larotrectinib sulfate (BAY 2757556, LOXO-101) caused the adverse event:**

**BLOOD AND LYMPHATIC SYSTEM DISORDERS** - Leukocytosis

**CARDIAC DISORDERS** - Atrial fibrillation; Atrioventricular block first degree; Cardiac disorders - Other (left ventricular dysfunction); Pericardial effusion

**ENDOCRINE DISORDERS** - Hypothyroidism

**EYE DISORDERS** - Eye pain; Periorbital edema; Watering eyes

**GASTROINTESTINAL DISORDERS** - Abdominal distension; Ascites; Dry mouth; Dyspepsia; Dysphagia; Gastrointestinal disorders - Other (enterocutaneous fistula); Gastrointestinal disorders - Other (gastrointestinal obstruction); Gastrointestinal disorders - Other (teething); Oral pain; Small intestinal obstruction; Small intestinal perforation

**GENERAL DISORDERS AND ADMINISTRATION SITE CONDITIONS** - Chills; Facial pain; Flu like symptoms; Multi-organ failure; Pain

**HEPATOBILIARY DISORDERS** - Hepatobiliary disorders - Other (bile duct obstruction); Hepatobiliary disorders - Other (hepatic function abnormal); Hepatobiliary disorders - Other (jaundice cholestatic)

**IMMUNE SYSTEM DISORDERS** - Allergic reaction

**INFECTIONS AND INFESTATIONS** - Hepatitis viral; Laryngitis; Lung infection; Sepsis; Skin infection; Upper respiratory infection; Urinary tract infection; Vaginal infection; Viremia; Wound infection

**INJURY, POISONING AND PROCEDURAL COMPLICATIONS** - Fall

**INVESTIGATIONS** - Alkaline phosphatase increased; Blood bilirubin increased; Ejection fraction decreased; Electrocardiogram QT corrected interval prolonged; Investigations - Other (hepatic cytolysis); Lipase increased; Lymphocyte count decreased; Serum amylase increased; Weight loss; White blood cell decreased

**METABOLISM AND NUTRITION DISORDERS** - Anorexia; Dehydration; Hypercalcemia; Hyperglycemia; Hypernatremia; Hypertriglyceridemia; Hyperuricemia; Hypoalbuminemia; Hypokalemia; Hypomagnesemia; Hyponatremia; Hypophosphatemia

**MUSCULOSKELETAL AND CONNECTIVE TISSUE DISORDERS** - Arthralgia; Back pain; Flank pain;

Generalized muscle weakness; Joint range of motion decreased; Musculoskeletal and connective tissue disorder - Other (muscle twitching); Musculoskeletal and connective tissue disorder - Other (musculoskeletal stiffness); Musculoskeletal and connective tissue disorder - Other (pain in jaw); Pain in extremity

**NEOPLASMS BENIGN, MALIGNANT AND UNSPECIFIED (INCL CYSTS AND POLYPS)** - Neoplasms benign, malignant and unspecified (incl cysts and polyps) - Other (acute myeloid leukemia); Neoplasms benign, malignant and unspecified (incl cysts and polyps) - Other (bile duct adenocarcinoma); Neoplasms benign, malignant and unspecified (incl cysts and polyps) - Other (glioma, glioblastoma multiforme); Neoplasms benign, malignant and unspecified (incl cysts and polyps) - Other (malignant neoplasm progression, neoplasm progression); Neoplasms benign, malignant and unspecified (incl cysts and polyps) - Other (metastases to central nervous system)

**NERVOUS SYSTEM DISORDERS** - Ataxia; Depressed level of consciousness; Dysarthria; Dysesthesia; Dysgeusia; Edema cerebral; Extrapyramidal disorder; Headache; Memory impairment; Nervous system disorders - Other (motor dysfunction); Peripheral sensory neuropathy; Somnolence; Spinal cord compression; Syncope

**PSYCHIATRIC DISORDERS** - Agitation; Confusion; Delirium; Personality change; Restlessness

**RENAL AND URINARY DISORDERS** - Hematuria; Proteinuria

**RESPIRATORY, THORACIC AND MEDIASTINAL DISORDERS** - Hypoxia; Nasal congestion; Oropharyngeal pain; Pleural effusion; Productive cough; Respiratory failure; Respiratory, thoracic and mediastinal disorders - Other (hypoventilation); Sneezing; Voice alteration; Wheezing

**SKIN AND SUBCUTANEOUS TISSUE DISORDERS** - Hyperhidrosis; Pruritus; Rash maculo-papular

**VASCULAR DISORDERS** - Hot flashes; Hypertension; Hypotension; Thromboembolic event

**Note:** Larotrectinib sulfate (BAY 2757556, LOXO-101) in combination with other agents could cause an exacerbation of any adverse event currently known to be caused by the other agent, or the combination may result in events never previously associated with either agent.

#### 9.1.10 Agent Ordering and Agent Accountability

NCI-supplied agents may be requested by eligible participating Investigators (or their authorized designee) at each participating institution. The CTEP-assigned protocol number must be used for ordering all CTEP-supplied investigational agents. The responsible investigator at each participating institution must be registered with CTEP, DCTD through an annual submission of FDA Form 1572 (Statement of Investigator), NCI Biosketch, Agent Shipment Form, and Financial Disclosure Form (FDF). If there are several participating investigators at one institution, CTEP-supplied investigational agents for the study should be ordered under the name of one lead participating investigator at that institution.

**Note:** No starter supplies will be provided. **Drug orders of larotrectinib should be placed with CTEP after enrollment and treatment assignment to APEC1621A with consideration for timing of processing and shipping to ensure receipt of drug supply prior to start of protocol therapy.** If expedited shipment is required, sites should provide an express courier account through the Online Agent Order Processing (OAOP) application. Provide the patient ID number in the comment box when submitting an order request.

#### 9.1.11 Clinical Drug Request

Submit agent requests through the PMB Online Agent Order Processing (OAOP) application. Access to OAOP requires the establishment of a CTEP Identity and Access Management (IAM) account and the maintenance of an “active” account status, “current” password, and active person registration status. For questions about drug orders, transfers, returns, or accountability call or email PMB anytime. Refer to the PMB’s website for specific policies and guidelines related to agent management.

#### 9.1.12 Agent Inventory Records

The investigator, or a responsible party designated by the investigator, must maintain a careful record of the receipt, dispensing and final disposition of all agents received from the PMB using the appropriate NCI Investigational Agent (Drug) Accountability Record (DARF) available on the CTEP forms page. Store and maintain separate NCI Investigational Agent Accountability Records for each agent, strength, formulation and ordering investigator on this protocol.

#### 9.1.12 Investigator Brochure Availability

The current versions of the IB(s) for the agents will also be accessible to site investigators and research staff through the PMB Online Agent Order Processing (OAOP) application. Access to OAOP requires the establishment of a CTEP IAM account and the maintenance of an “active” account status, a “current” password, and active person registration status. Questions about IB access may be directed to the PMB IB coordinator via email.

## 10.0 CRITERIA FOR REMOVAL FROM PROTOCOL THERAPY AND OFF STUDY CRITERIA

### 10.1 Criteria for Removal from Protocol Therapy

- a) Clinical (including physical examination or serum tumor markers) or radiographic evidence of progressive disease (See [Section 12](#)).
- b) Adverse Events requiring removal from protocol therapy (See [Section 6](#)).
- c) Refusal of protocol therapy by patient/parent/guardian
- d) Non-compliance that in the opinion of the investigator does not allow for ongoing participation.
- e) Completion of 26 cycles of therapy.
- f) Physician determines it is not in the patient's best interest.
- g) Repeated eligibility laboratory studies (CBC with differential, bilirubin, ALT (SGPT) or serum creatinine) are outside the parameters required for eligibility prior to the start of protocol therapy (See [Section 8.1](#)).
- h) Study is terminated by Sponsor.
- i) Pregnancy
- j) Patient did not receive protocol treatment after study enrollment.

**Patients who are removed from protocol therapy during cycle 1 should continue to have the required observations in [Section 8.1](#) until the originally planned end of the cycle or until all adverse events have resolved per [Section 13.4.4](#), whichever happens LATER. The only exception is with documentation of the patient's withdrawal of consent from the APEC1621SC screening protocol. Patients who are removed from protocol therapy in subsequent cycles should have the necessary observations to ensure adequate clinical care.**

### 10.2 Follow-Up Data Submission and APEC1621SC Off Study Criteria

Patients who are off subprotocol therapy will initially be followed on the therapeutic subprotocol for a 30-day period. During follow-up on the subprotocol, ongoing adverse events, or adverse events that emerge after the patient is removed from protocol therapy, but within 30 days of the last dose of investigational agent, must be followed and reported via RAVE and CTEP-AERS (if applicable). Upon completion of subprotocol follow-up period, the patient will continue to be followed on the APEC1621SC screening protocol. Follow-up data submission will occur until one of the APEC1621SC Off Study Criteria is

met (See Section 10 of APEC1621SC for details), consent is withdrawn or the patient dies or is lost to follow-up.

## 11.0 STATISTICAL AND ETHICAL CONSIDERATIONS

### 11.1 Sample Size and Study Duration

APEC1621A will require a minimum of 20 evaluable patients, and a maximum of 49 patients, allowing for 15% inevaluable. Assuming an enrollment rate of 4-9 biomarker positive patients per year, the primary cohort of this subprotocol is expected to be completed within 2.7-6 years.

### 11.2 Dosing Considerations

Please see [Section 5.1](#) for a specific discussion of the dosing of LOXO-101 (larotrectinib) to be used in this study. Please note that limited pharmacokinetic sampling may be done for patients enrolled on this arm.

### 11.3 Study Design

The primary cohort will employ a single stage A'Hern design of N=20. The agent will be deemed worthy of further study in the relevant subset of patients (i.e. biomarker positive in any histology, biomarker positive in a particular histology, etc) if the decision rule is met. Operating characteristics are shown below.

Cohort	N	Decision Rule	Alpha	Power
Primary biomarker positive	20	$\geq 3$ responses	10%	90%

Histology-specific biomarker positive expansion cohorts will, by definition, be deemed worthy of further study, since they will have at least 3 responses. The table below shows 90% confidence intervals (Wilson method) for a range of observable response rates.

Cohort Size	Observed Response Rate	90% Confidence Interval
10	30%	13% - 56%
10	40%	19% - 65%
10	50%	27% - 73%

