## 2.4 **Larotrectinib Activity in NTRK Fusion Positive Malignancies**

2.4.1 As of a November 10, 2016 data cutoff, 59 patients with refractory solid tumors had been enrolled and treated with single agent LOXO-101, including eight patients with cancers harboring NTRK fusions. Seven patients with NTRK fusion cancers were on study sufficiently long for an efficacy assessment, while an eighth NTRK fusion patient had been recently enrolled and was not yet evaluated for response. Six of the seven efficacy evaluable patients achieved a confirmed partial response, as defined by standard RECIST criteria. The seventh patient, as previously reported, demonstrated clear radiographic tumor regressions, including in the central nervous system, and remains on study, but had not met the threshold required for a RECIST response. All responders remained in response, with one patient in cycle 22, one patient in cycle 19, one patient in cycle 18, two patients in cycle 15 and one patient in cycle 11. Each cycle is 28 days, or approximately one month.

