#### 11.3.2 Histology-Specific Biomarker Positive Expansion Cohorts:

If at any time  $\geq 3$  patients in the primary cohort with the same histology show signs of objective response (CR/PR according to the response criteria in [Section 12.3](#)),

a histology-specific biomarker positive expansion cohort will open after the primary cohort is completed to up to 7 evaluable patients for a total sample size of 10 evaluable biomarker positive patients with that histology. This will allow us to estimate more precisely the activity in biomarker positive patients of that histology. See [Appendix VIII](#) for a list of target tumor histologies.

We will open up to 3 such expansion cohorts for biomarker positive patients (i.e., if 3 histologies have  $\geq 3$  responses, we will open a total of 3 expansion cohorts as described above). Note that this can only happen if the response rate in the primary cohort is at least 45% (9/20) and there cannot be more than 21 additional evaluable patients in total for these expansion cohorts.

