#### 11.4 **Methods of Analysis**

Response criteria are described in [Section 12](#). A responder is defined as a patient who achieves a best response of PR or CR on the study. Response rates will be calculated as the percent of evaluable patients who are responders, and confidence intervals will be constructed using the Wilson score interval method. Decision making for A'Hern design cohorts will follow rules described above.

Toxicity tables will be constructed to summarize the observed incidence by type of toxicity and grade. A patient will be counted only once for a given toxicity for the worst grade of that toxicity reported for that patient. Toxicity information recorded will include the type, severity, time of onset, time of resolution, and the probable association with the study regimen.

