#### 11.5 **Evaluability for Response**

Any eligible patient who is enrolled and receives at least one dose of protocol therapy will be considered evaluable for response. Any patient who receives non-protocol anti-cancer therapy during the response evaluation period will be considered a non-responder for the purposes of the statistical rule, unless they show an objective response prior to receiving the non-protocol anti-cancer therapy (in which case they will be considered a responder). Patients who demonstrate a complete or partial response confirmed by central review will be considered to have experienced a response. When opening expansion cohorts, the evaluation period for determination of best response will be 6 treatment cycles. All other patients will be considered non-responders. Patients who are not evaluable for response evaluation may be replaced for the purposes of the statistical rule. All patients considered to have a response (CR or PR) must have imaging studies reviewed centrally at the COG. Centers will be notified by the COG about requests for scans of patients with stable disease. Preliminary assessment of activity using institutionally provided tumor measurements will be entered into CDUS quarterly. The central review by COG will be provided as the final reviewed assessment of response when such becomes available.

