### 12.3.1 Definitions

#### 12.3.1.1 Evaluable for objective response:

Eligible patients who receive at least one dose of protocol therapy will be considered evaluable for response. Evaluable patients who demonstrate a complete or partial response confirmed by central review before receiving non-protocol anti-cancer therapy will be considered a responder. All other evaluable patients will be considered non-responders.

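### Expansion-cohort response rates include the responders that triggered expansion, so they are biased upward when activity is modest, and the plan neither says so nor reports the new patients separately

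*Combined protocol and SAP*

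**What the plan says.** Section 11.3.2 opens an expansion cohort if at least three "patients in the primary cohort with the same histology show signs of objective response (CR/PR according to the response criteria in" Section 12.3). Up to 7 further evaluable patients are then enrolled "for a total sample size of 10 evaluable biomarker positive patients with that histology". The stated purpose is estimation: "This will allow us to estimate more precisely the activity in biomarker positive patients of that histology".

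The cohort has no decision rule of its own. Section 11.3 says: "Histology-specific biomarker positive expansion cohorts will, by definition, be deemed worthy of further study, since they will have at least 3 responses". That holds only if the triggering responses are counted in the cohort. Directly below, a table for a cohort of 10 gives 90% Wilson intervals at observed rates of 30%, 40% and 50%.

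Section 11.4 has no separate method for expansion cohorts; for all response rates, "confidence intervals will be constructed using the Wilson score interval method". Section 11.5 adds: "When opening expansion cohorts, the evaluation period for determination of best response will be 6 treatment cycles". Section 12.3.1.1 defines who counts: "Evaluable patients who demonstrate a complete or partial response confirmed by central review before receiving non-protocol anti-cancer therapy will be considered a responder".

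I found nothing in Section 11 that says the expansion estimate or its interval is conditional on the trigger, and no separate result for the newly enrolled patients.

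**The concern.** A histology reaches the expansion analysis because it already produced three or more responses, and those responses are then used again in the estimate. Given that a cohort opens, the pooled rate has a floor of 30%. Its expectation exceeds the true rate, and the Wilson interval no longer has its nominal coverage. The table starts at 30% without saying that this is the lowest value the cohort can show.

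Estimation is the cohort's only purpose, so the rate and interval are its whole product. Where the drug has modest activity in a histology, the planned output would overstate that activity, and a reader could not tell how much came from the triggering responders. For example, 3 of 3 in the primary cohort followed by 0 of 7 new patients would be reported as 30% (13% to 56%), while the new patients alone give 0/7 (0% to 28%).

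**Working it through.** **Inputs from the plan.** Trigger of at least 3 responders in one histology and a total of 10 (11.3.2); 90% Wilson intervals (11.3, 11.4); null rate 5%, target rate 25%, rule of at least 3 of 20 (11.3.1).

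**Assumptions.** k, the number of primary-cohort patients with the triggering histology, is not in the documents; I use 3, 5 and 8. The total is exactly 10, and the true rate p is the same for primary and new patients of that histology.

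**Reproducing the plan's figures.** The Wilson interval is [p̂ + z²/2n ± z√(p̂(1−p̂)/n + z²/4n²)] / (1 + z²/n), with z = 1.645 and n = 10. It gives:
- 3/10: 12.7% to 55.8%
- 4/10: 19.4% to 64.8%
- 5/10: 26.9% to 73.1%

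All three rows of the table agree after rounding. The primary rule has an exact type I error of 7.55% and power of 90.9%, consistent with the stated 10% and 90%.

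**Effect of the trigger.** Let X1 ~ Bin(k, p) be responders among the k primary patients, X2 ~ Bin(10−k, p) responders among the new patients, and S = X1 + X2. The cohort exists only if X1 ≥ 3. By exact enumeration:
- opening = P(X1 ≥ 3)
- expected reported rate = E[S/10 | X1 ≥ 3]
- coverage = P(the Wilson interval for S/10 contains p | X1 ≥ 3)

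Hand check at k = 3, p = 0.25:
- Opening is 0.25³ = 1.6%.
- The expected rate is (3 + 7 × 0.25)/10 = 47.5%.
- The lower limit is below 25% at 3/10 and 4/10 but above it at 5/10 (26.9%). The interval therefore covers 25% only if X2 ≤ 1, and P(Bin(7, 0.25) ≤ 1) = 0.445.

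Results for k = 3 / 5 / 8:

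| True rate | Opening (%) | Bias given opening (points) | Coverage given opening (%) | Unselected coverage, n=10 (%) |
|---|---|---|---|---|
| 10% | 0.1 / 0.9 / 3.8 | +27.0 / +25.5 / +23.4 | 0 / 0 / 0 | 93 |
| 25% | 1.6 / 10.4 / 32.1 | +22.5 / +19.1 / +14.5 | 44 / 57 / 76 | 87 |
| 40% | 6.4 / 31.7 / 68.5 | +18.0 / +13.1 / +7.3 | 71 / 84 / 92 | 90 |
| 50% | 12.5 / 50.0 / 85.5 | +15.0 / +9.4 / +3.8 | 77 / 89 / 94 | 89 |
| 75% | 42.2 / 89.7 / 99.6 | +7.5 / +2.2 / +0.2 | 85 / 90 / 87 | 87 |

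At a true 25%, every miss is an interval wholly above the truth: 56% / 43% / 24% of opened cohorts, against 7.8% for an unselected sample of 10. The lowest attainable lower limit is 12.7%, so no true rate below that can be covered. At a true 85% the bias is +4.5 / +0.6 / 0.0 points and coverage is at least 95%.

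**Error rates.** Opening any cohort needs at least 3 responses among the 20 primary patients. At the 5% null the chance of that is at most 7.55%, so the automatic positive label does not raise the false-positive rate.

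**The case against.** **Partly disclosed already.** Section 11.3 says openly that the positive label is automatic and that at least 3 responses are guaranteed; a reader can work out the 30% floor. This stands for the label and the floor, but not for the bias in the estimate and interval, which the plan does not mention.

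**The floor is not absolute.** The trigger wording in 11.3.2 is loose, and 11.5 treats institutional measurements as preliminary and central review as final. A triggering response could later be reversed. That is possible, but 11.5 and 12.3.1.1 count only centrally confirmed responses, and 11.3 itself takes at least 3 as given.

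**The 90% level is inferred.** Section 11.4 names no confidence level; 90% comes from the table in 11.3. This is correct, but it does not affect the bias.

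**Low materiality.** No test depends on these cohorts. The worst coverage needs 3 of 3 responses at a true 25%. The joint probability of opening and missing at 25% is 0.9% / 4.4% / 7.8%, below the 13.4% miss rate of an unselected interval. Section 2.4 points to high activity: "Six of the seven efficacy evaluable patients achieved a confirmed partial response". All this stands and keeps the point minor. However, the expansion result is reported only for cohorts that open, so conditional performance is what its reader faces. High activity overall also does not guarantee it in each of the many tumor types in Appendix VII.

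**New patients alone are often the worse estimator.** This is true in much of the range, and is why the pooled result should stay.

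**Conclusion.** The concern holds, as a minor point of analysis and reporting. The pooled estimate is biased upward given opening, and the plan provides neither a caveat nor the data split that would let a reader judge it. The effect matters where true activity in the histology is modest and few primary-cohort patients carry it: about +15 to +23 points at a true 25% for k between 3 and 8. It is small at 75% or above, and at k = 8 coverage is already above nominal for true rates of 40% and 50%. These sizes rest on the assumed k, a common true rate within the histology, a total of exactly 10, and triggering responses that survive central review. The Wilson table is arithmetically correct for an unselected sample, and the primary N=20 conclusion is untouched.

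**What to change.** In Sections 11.3.2 and 11.4, keep the pooled result for 10 patients. Beside it, report the response rate and 90% Wilson interval for the patients enrolled after the primary cohort is complete. Next to the table in 11.3, state that:
1. the pooled rate and interval are conditional on at least 3 triggering responses and are biased upward when activity is modest;
2. 30% is the lowest attainable value;
3. the positive label follows from the trigger and not from the expansion data.

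A selection-conditioned estimate and interval could be added as a sensitivity analysis but is not required.

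The cost is three sentences and one output line per cohort, with no extra patients. The drawback is imprecision: 3/7 gives 19% to 71%, and with only two new patients (k = 8) 0/2 gives 0% to 57%. For k = 3 / 5 / 8 at a true 25%, the new-patient interval averages 45 / 50 / 64 points wide, against 45 pooled. Its root mean squared error is 0.164 / 0.194 / 0.306 against 0.252 / 0.218 / 0.172 pooled, so it is better at k = 3 and 5 but worse at 8. At 40% it is better only at k = 3 (0.185 against 0.222), and at 75% at none of the three. The two results should therefore be shown together.
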